5.3 Concomitant Medications/Treatments

Patients should avoid PPI or other drugs that inhibit (i.e. itraconazole, clarithromycin, atazanavir, indinavir, nefazodone, nelfinavir, voriconazole) or induce (i.e. rifampin) CYP3A4. Specifically, taking pazopanib with simvastatin has showed to increase the risk of hepatotoxicity. So, **simvastatin has to be stopped prior to/at subject registration.**

5.4 Duration of Therapy

In the absence of treatment delays due to adverse events, treatment may continue until one of the following criteria apply:

- Disease progression as defined in Section 7.0
- Inter-current illness that prevents further administration of treatment as deemed appropriate by treating physician.
- Unacceptable adverse event(s) as defined in Section 8.0

- Patient voluntarily withdraws from treatment OR changes in the patient's condition render the patient unacceptable for further treatment in the judgment of the investigator.
- Completion of therapy with pazopanib with low fat meal for 12 weeks. Patients could then go onto standard therapies, including pazopanib given without food/low fat meal.

5.5 Off Treatment Criteria

Patients will be removed from protocol therapy when any of the criteria listed in Section 5.4 apply. Document in the source the reason for ending protocol therapy and the date the patient was removed from treatment. All patients who discontinue treatment should comply with protocol specific follow-up procedures as outlined in Section 5.6. The only exception to this requirement is when a subject withdraws consent for all study procedures or loses the ability to consent freely.

5.6 Duration of Follow-Up

Patients will be followed for 28 days after removal from treatment or until death, whichever occurs first. Patients removed from treatment for unacceptable adverse events will be followed until resolution or stabilization of the adverse event (Grade 1 or lower).

5.7 Off Study Criteria

Patients can be taken off study at any time at their own request, or they may be withdrawn at the discretion of the investigator for safety, behavioral or administrative reasons. The reason(s) for discontinuation from study will be documented and may include:

- 5.7.1 Patient withdraws consent (termination of treatment and follow-up);
- 5.7.2 Loss of ability to freely provide consent through imprisonment or involuntary incarceration for treatment;
- 5.7.3 Patient is unable to comply with protocol requirements;
- 5.7.4 Treating physician judges continuation on the study would not be in the patients best interest;
- 5.7.5 Patient becomes pregnant (pregnancy to be reported along same timelines as a serious adverse event);
- 5.7.6 Development of second malignancy (except for basal cell carcinoma or squamous cell carcinoma of the skin) that requires treatment or which would interfere with this study (per PI);
- 5.7.7 Termination of the study by The University of Michigan;
- 5.7.8 Patient completes protocol treatment and follow-up criteria.

5.8 Patient Replacement

Subjects who are removed or withdraw consent from the study will not be replaced.

6.0 STUDY PROCEDURES

6.1 Pharmacokinetic Assessment

Analysis of the samples for plasma concentration of pazopanib by the Pharmacokinetics Core at the College of Pharmacy of the University of Michigan at various time points (please refer to Section 10.0 for details) will be per previously established assays⁶.

6.2 Screening/Baseline Procedures

Assessments performed exclusively to determine eligibility for this study will be done only after obtaining informed consent. Assessments performed for clinical indications (not exclusively to determine study eligibility) may be used for baseline values even if the studies were done before informed consent was obtained.

All screening procedures must be performed within 28 days prior to registration unless otherwise stated. The screening procedures include:

6.2.1 *Informed Consent*

6.2.2 *Medical history*

Complete medical and surgical history, history of infections

6.2.3 *Demographics*

Age, gender, race, ethnicity

6.2.4 *Review subject eligibility criteria*

6.2.5 *Review previous and concomitant medications*

6.2.6 *Physical exam including vital signs, height and weight*

Vital signs (temperature, pulse, respirations, blood pressure), height, weight

6.2.7 *Performance status*

Performance status evaluated prior to study entry according to Appendix 4.

6.2.8 *Adverse event assessment*

Baseline adverse events will be assessed. See Section 8.0 for Adverse Event monitoring and reporting.

6.2.9 *Hematology*

Complete blood count with differential, platelet count.

6.2.10 *Serum chemistries*

Comprehensive metabolic panel (CMP) to include: albumin, alkaline phosphatase, ALT/SGPT, AST/SGOT, BUN, creatinine, electrolytes (sodium, potassium, calcium, chloride, bicarbonate, magnesium), glucose, and total bilirubin.

6.2.11 *Pregnancy test (for all females)*

Urine or serum.

6.2.12 *Tumor assessment*

To be performed with computed tomography or MRI of chest, abdomen and pelvis; CT or MRI of the brain.

For all axial imaging studies, intravenous contrast administration is preferred if judged safe by treating investigator.

6.2.13 **Other**

- A baseline transthoracic echocardiogram will be obtained to assess baseline LVEF
- 12-lead ECG will be obtained in triplicate at least 5 minutes apart from each other to determine QTc interval at baseline.
- A Urine Protein Creatinine ratio and TSH will also be obtained to evaluate for baseline proteinuria and hypothyroidism, respectively, as part of screening for the study.
 - Whole blood sample (10 mL) into EDTA-containing blood collection tube to be stored at the "Sample Preservation Freezer Facility"

6.3 **Procedures During Treatment**

6.3.1 **Day 1 of each cycle (e.g. C1 D1, C2 D1...etc. until C6 D1)**

- Physical exam, vital signs
- Hematology: Complete blood count with differential, platelet count.
- Serum chemistries: Comprehensive metabolic panel (CMP) to include: albumin, alkaline phosphatase, ALT/SGPT, AST/SGOT, BUN, creatinine, electrolytes (sodium, potassium, calcium, chloride, and bicarbonate, magnesium), glucose, and total bilirubin.
- Review of toxicities (refer to section 5.2).
- Review of concomitant medications.
- 12-lead ECG will be obtained in triplicate at least 5 minutes apart from each other to determine QTc interval.

6.3.2 **Procedures for Cycle 1 Day 1, Cycle 2 Day 1 and Cycle 3 Day 1 ONLY**

- Patient will be given pazopanib to take by mouth with low fat meal by research/MCRU staff who will record time.
- Whole blood samples (5mL each) will be collected from patient into EDTA-containing blood collection tubes at specified times per section 10.0.

6.3.3 **EOT visit (end of cycle 6 ± 7 days)**

- End of Treatment (EOT) visit will be post 12 weeks of protocol therapy
- CT chest, abdomen, pelvis with or without intravenous contrast (with intravenous contrast preferred if clinically felt safe to do so by treating investigator). MRI abdomen pelvis can be substituted for CT abdomen pelvis.
- A repeat transthoracic echocardiogram will be obtained **once** to re-assess LVEF after 12 weeks of therapy.
- A Urine Protein Creatinine ratio and TSH will also be obtained to evaluate for baseline proteinuria and hypothyroidism, respectively, as part of screening for the study. If TSH is abnormal, add-on labs of free T3 and free T4 may be added to blood sample per treating investigator discretion.
- 12-lead ECG will be obtained in triplicate at least 5 minutes apart from each other to determine QTc interval.
- Whole blood sample (10 mL) into EDTA-containing blood collection tube to be stored at the "Sample Preservation Freezer Facility"

6.3.4 **28 days after EOT visit (± 7 days)**

- Physical exam, vital signs

- Hematology: Complete blood count with differential, platelet count.
- Serum chemistries: Comprehensive metabolic panel (CMP) to include: albumin, alkaline phosphatase, ALT/SGPT, AST/SGOT, BUN, creatinine, electrolytes (sodium, potassium, calcium, chloride, bicarbonate, magnesium), glucose, and total bilirubin
- Toxicity check

6.4 Time and Events Table/Study Calendar

| Study Calendar | Screening (within 28 d) | C1 D1 ± 3d | C2 D1 ± 3d | C3 D1 ± 3d... | C4/5/6 D1 ± 3d | EOT ±7d | 28 days after EOT ± 7d |
|--|-------------------------|------------|------------|---------------|----------------|-------------------|------------------------|
| Informed Consent | X | | | | | | |
| History and PE Weight | X | X | X | X | X | X | X |
| ECOG Performance Status | X | X | X | X | X | X | X |
| Toxicity Assessment | X | X | X | X | X | X | X |
| Patient Diaries (blood pressure logs and pill diary) | X | X | X | X | X | X | |
| Dietician visit | | X | | | | | |
| CBC with differential, platelet count | X | X | X | X | X | X | X |
| COMP | X | X | X | X | X | X | X |
| TSH | X | | | | | X | |
| Concomitant Medication Review | X | X | X | X | X | X | X |
| 12-lead ECG in triplicate | X | X | X | X | X | X | |
| Transthoracic Echocardiogram with LVEF estimation | X | | | | | X | |
| PK samples* | | X | X | X | | | |
| Blood sample for storage at SPFF | X | | | | | X | |
| Urine Protein Creatinine ratio | X | | | | | X | |
| CT chest, abdomen, pelvis | X | | | | | X | |
| CT or MR head | X | | | | | X (if clinically) | |

| | | | | | | | |
|-----------------------------|---|---|--|--|--|---------------|--|
| | | | | | | indicat ed | |
| Pregnancy Test** | X | | | | | | |
| Pazopanib with low fat meal | | X | | | | | |

*Please refer to section 10.0

**Serum or urine pregnancy test for all females

*** Sample Preservation Facility (U of M- MSRB3) .

7.0 MEASUREMENT OF EFFECT

7.1 Antitumor Effect- Solid Tumors

Response and progression will be evaluated in this study using the new international criteria proposed by the Response Evaluation Criteria in Solid Tumors (RECIST 1.1) Committee]. The largest diameter (unidimensional measurement) of the tumor lesions are used in the RECIST v1.1 criteria.

7.1.1 Definitions

Evaluable for toxicity. All patients will be evaluable for toxicity from the time of their first dose of study drug.

Evaluable for objective response. Only those patients who have measurable disease present at baseline, have received at least 4 cycles of therapy, and have had their disease re-evaluated will be considered evaluable for response. These patients will have their response classified according to the definitions stated below. (Note: Patients who exhibit objective disease progression prior to the end of cycle 1 will also be considered evaluable.)

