1.3 Study Design/Schema

Registered subjects will take pazopanib by mouth with a low-fat meal (**containing less than 400 calories and less than 20% fat or 10 grams per meal**) approximately, some sample meals are described in appendix 1) every day in 14 day cycles, for a total of 6 cycles, with a starting dose of 400 mg and adjusted for the next cycle (dose level +1: 600 mg; dose level +2: 800 mg; dose level -1: 200 mg) based on toxicity assessment during or at the end of each cycle. No dose re-escalations are permitted. Imaging will be performed post 12 weeks of treatment.

An interim analysis for safety will be performed after 8 subjects have completed at least 2 cycles (4 weeks) of therapy.

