7.1.4.3 Evaluation of Best Overall Response

The best overall response is the best response recorded from the start of the treatment until disease progression/recurrence (taking as reference for progressive disease the smallest measurements recorded since the treatment started). The patient's best response assignment will depend on the achievement of both measurement and confirmation criteria.

| Target Lesions | Non-Target Lesions | New Lesions | Overall Response | Best Response for this Category Also Requires: |
|----------------|--------------------|-------------|------------------|--|
| CR | CR | No | CR | ≥4 wks. confirmation |
| CR | Non-CR/SD | No | PR | ≥4 wks. confirmation |
| PR | Non-PD | No | PR | |
| SD | Non-PD | No | SD | documented at least once ≥4 wks. from baseline |
| PD | Any | Yes or No | PD | no prior SD, PR or CR |
| Any | PD* | Yes or No | PD | |
| Any | Any | Yes | PD | |

* In exceptional circumstances, unequivocal progression in non-target lesions may be accepted as disease progression.

Note: Patients with a global deterioration of health status requiring discontinuation of treatment without objective evidence of disease progression at that time should be reported as “*symptomatic deterioration*”. Every effort should be made to document the objective progression even after discontinuation of treatment.

Note: If subjects respond to treatment and are able to have their disease resected, the patient’s response will be assessed prior to the surgery.

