7.2 Safety/Tolerability

Analyses will be performed for all patients having received at least one dose of study drug (pazopanib). The study will use the CTCAE version 4.0 for reporting of non-hematologic adverse events (<http://ctep.cancer.gov/reporting/ctc.html>) and modified criteria for hematologic adverse events.

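### The response-evaluable rule in 7.1.1 drops patients whose progression is documented after cycle 1 and who stop before receiving four cycles, although they are known non-responders at week 12

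*Combined protocol and SAP*

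**What the plan says.** - **Who counts for response (7.1.1).** Measurable baseline disease is needed, and only patients who "have received at least 4 cycles of therapy, and have had their disease re-evaluated will be considered evaluable for response". One exception follows: "Patients who exhibit objective disease progression prior to the end of cycle 1 will also be considered evaluable".
- **When treatment ends (5.4, 5.5).** One of the criteria for ending protocol therapy is "Disease progression as defined in Section 7.0".
- **Replacement (5.8).** "Subjects who are removed or withdraw consent from the study will not be replaced".
- **Scans (1.3, 6.3.3, 6.4).** "Imaging will be performed post 12 weeks of treatment", and "End of Treatment (EOT) visit will be post 12 weeks of protocol therapy". The calendar in 6.4 lists no body scan between screening and that visit.
- **Progression after stopping (7.1.4.3).** For patients who stop because of symptomatic deterioration: "Every effort should be made to document the objective progression even after discontinuation of treatment".
- **The response endpoint (11.1).** CR plus PR at 12 weeks, with exact binomial 95% intervals. No denominator is given.
- **The one-dose analysis set (7.2).** "Analyses will be performed for all patients having received at least one dose of study drug (pazopanib". This stands under safety and tolerability.

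**The concern.** Membership of the response set depends partly on outcome. Without treatment delays, progression documented on day 12 is counted through the exception. Progression found on day 60 is counted because four cycles are complete and disease has been re-evaluated. Progression documented on day 30 that ends treatment is not counted. No reason is given for treating these three patients differently, and the exception itself shows that the authors regard an early progressor as informative.

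A patient with documented progression cannot be a responder at week 12 under 11.1. Removing that patient lowers the denominator and leaves the numerator alone, so the reported proportion can only rise. Response is the pilot's main efficacy figure, and 11.2 says that a larger study, which would also address efficacy, may follow from these data.

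**Working it through.** **The plan's own figures.** Section 11.1 tabulates exact 95% intervals for 16 patients. The Clopper-Pearson method gives 0.16-30.23% for 1/16, 1.55-38.35% for 2/16, 4.05-45.65% for 3/16, 15.20-64.57% for 6/16 and 24.65-75.35% for 8/16. All agree with the printed limits to within 0.1 percentage point, so the same method is used below.

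**The gap in days.** Cycles last 14 days (1.3). Without delays, cycle 1 ends on day 14, cycle 3 on day 42 and cycle 4 on day 56. The plan does not say whether receiving four cycles means starting or completing the fourth.
- Progression documented on days 15-42 that ends treatment fails the rule on either reading.
- On days 43-56 it fails only if the fourth cycle must be completed.
- Dose holds would shift these days.

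**Effect of dropping d non-responders.** With r responders among 16 treated, the proportion moves from r/16 to r/(16 - d), a factor of 16/(16 - d). The documents do not give d. For illustration, the 30% response rate in 1.1 gives 0.30 x 16 = 4.8, taken as r = 5:

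| d | Proportion | 95% CI | Factor |
|---|---|---|---|
| 0 | 5/16 = 31.3% | 11.0-58.7 | 1.00 |
| 1 | 5/15 = 33.3% | 11.8-61.6 | 16/15 = 1.07 |
| 2 | 5/14 = 35.7% | 12.8-64.9 | 16/14 = 1.14 |

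**How many patients might fall in the gap.** Assume exponential PFS, S(t) = exp(-ln 2 x t / median), with 30.44 days per month and the pazopanib medians in 1.1 (7.4, 9.2 and 11.1 months). The expected numbers of 16 are 16 x [S(14) - S(42)] and 16 x [S(14) - S(56)]:

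| Median (months) | S(14) | S(42) | S(56) | Days 15-42 | Days 15-56 |
|---|---|---|---|---|---|
| 7.4 | 0.958 | 0.879 | 0.842 | 1.3 | 1.9 |
| 9.2 | 0.966 | 0.901 | 0.871 | 1.0 | 1.5 |
| 11.1 | 0.972 | 0.917 | 0.891 | 0.9 | 1.3 |

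These are upper values under the model. Progression that nobody detects before week 12 leaves the patient on treatment and evaluable, and the documents do not say how often unscheduled imaging or examination would find it. With d anywhere from 0 to 1.9, the factor runs from 1.00 to 16/14.1 = 1.13.

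**Sensitivity to the medians.** The population in 1.1 had no prior therapy or one cytokine therapy, whereas 3.1.5 allows up to three prior VEGF or VEGFR lines. At an assumed pessimistic median of 4.2 months, the figure for days 15-56 is about 3.0 of 16, again before allowing for non-detection.

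**The case against.** The strongest reply is that the effect is small and the endpoint modest. No scan is scheduled before week 12, so a patient enters the gap only through unscheduled imaging or examination. Response is secondary, with no test, threshold or go/no-go rule, in a convenience sample. A shift of 35.7 - 31.3, about 4.5 points, is little beside an interval about 48 points wide. All of this stands, and it sets the severity.

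It might also be said that other sections repair the rule. They do not. The 16-patient intervals in 11.1 illustrate the toxicity and feasibility endpoints. The one-dose set in 7.2 is for safety. Section 7.1.4.3 asks for later progression to be documented after symptomatic deterioration, but 7.1.1 does not readmit the patient.

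Four stronger readings are tempting and are not supported:
- **That everyone progressing up to the end of cycle 4 is dropped.** Days 43-56 depend on what receiving a cycle means.
- **That the rule as a whole biases response upward.** Patients who stop early for toxicity or withdrawal are also dropped, usually with unknown response, and the documents do not settle the direction for them.
- **That an off-schedule response in a dropped patient reverses the direction.** Section 11.1 counts response at 12 weeks, so such a response is not in its numerator. Under the best-overall-response definition in 7.1.4.3 a response before progression could count, so the term known non-responder is tied to the 11.1 endpoint.
- **That the 4-week confirmation rule lowers the CR+PR total.** An unconfirmed disappearance of target lesions still meets the PR definition in 7.1.4.1, and the row in 7.1.4.3 for target PR without non-target progression requires no confirmation. Only the split between CR and PR is affected.

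**Conclusion.** The concern holds in narrow form and is minor. Followed as written, 7.1.1 removes patients with progression documented after cycle 1 who stop before receiving four cycles, and for them the bias in the week-12 response proportion is upward. The likely size is zero to two patients of 16, a factor of 1.00 to about 1.13. This rests on exponential PFS, on the medians in 1.1 carrying over to this population, and on no treatment delays. Heavier pretreatment could raise the number; non-detection before week 12 lowers it. Safety and feasibility conclusions are unaffected.

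**What to change.** - **7.1.1:** extend the exception to objective progression documented at any time before the week-12 scan, counted as non-response. Say whether receiving four cycles means starting or completing the fourth.
- **11.1:** state the response denominator. Also report the proportion among all patients who received at least one dose, the set 7.2 already uses and for whom 3.1.2 requires measurable disease. Count no documented week-12 response as non-response, and show how many had documented progression and how many had no post-baseline scan.
- **Separately:** reconcile the single post-baseline scan in 6.3.3 and 6.4 with the 4-week confirmation in 7.1.4.1 and 7.1.4.3, since a CR cannot be confirmed on the scheduled scans. Labelling week-12 response as unconfirmed would do.

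The cost is wording, with no added scan, visit or patient. The reported proportion may be lower, the all-treated figure may be too low if patients with unknown response would have responded, and an unconfirmed response is a weaker label.

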7.1.2 Disease Parameters

Measurable disease. Measurable lesions are defined as those that can be accurately measured in at least one dimension (longest diameter in the plane of measurement is to be recorded) with a minimum size of:

- 10mm by CT scan (irrespective of scanner type) for studies with a slice thickness of ≤ 5 mm or twice the slice thickness or MRI
- 10mm caliper measurement by clinical exam (lesions which cannot be accurately measured with calipers should be recorded as non-measurable)
- 20mm by chest X-ray (if clearly defined and surrounded by aerated lung)

All tumor measurements must be recorded in millimeters (or decimal fractions of centimeters).

Malignant lymph nodes: To be considered pathologically enlarged and measurable, a lymph node must be ≥ 15 mm in short axis when assessed by CT scan (CT scan slice thickness recommended to be no greater than 5 mm). At baseline and 28 days post therapy, only the short axis will be measured and followed.

Note: Tumor lesions that are situated in a previously irradiated area might or might not be considered measurable, and the conditions under which such lesions should be considered may be defined in the protocol when appropriate.

Non-measurable disease. All other lesions (or sites of disease), including small lesions (longest diameter <20 mm with conventional techniques or <10 mm using CT scan), are considered non-measurable disease. Bone lesions, leptomeningeal disease, ascites, pleural/pericardial effusions, lymphangitis cutis/pulmonis, inflammatory breast disease, abdominal masses (not followed by CT or MRI), and cystic lesions are all non-measurable.

Target lesions. All measurable lesions up to a maximum of 2 lesions per organ and 5 lesions in total should be identified as **target lesions** and recorded and measured at baseline. Target lesions should be selected on the basis of their size (lesions with the longest diameter), be representative of all involved organ, but in addition should be those that lend themselves to reproducible repeated measurements.

Lymph nodes merit special mention since they are normal anatomical structures which may be visible by imaging even if not involved by tumor. Pathological nodes which are defined as measurable and may be identified as target lesions must meet the criterion of a short axis of ≥ 15 mm by CT scan. Only the short axis of these nodes will contribute to the baseline sum. The short axis of the node is the diameter normally used by radiologists to judge if a node is involved by solid tumor. Nodal size is normally reported as two dimensions in the plane in which the image is obtained (for CT scan this is almost always the axial plane; for MRI the plane of acquisition may be axial, sagittal or coronal). The smaller of these measures is the short axis. For example, an abdominal node which is reported as being 20mm x 30mm has a short axis of 20mm and qualifies as a malignant, measurable node. In this example, 20mm should be recorded as the node measurement. All other pathological nodes (those with short axis ≥ 10 mm but <15 mm) should be considered non-target lesions. Nodes that have a short axis <10mm are considered non-pathological and should not be recorded or followed. A sum of the diameters (longest for non-nodal lesions, short axis for nodal lesions) for all target lesions will be calculated and reported as the baseline sum diameters. If lymph nodes are to be included in the sum, then as noted above, only the short axis is added into the sum. The baseline sum diameters will be used as reference to further characterize any objective tumor regression in the measurable dimension of the disease.

Non-target lesions. All other lesions (or sites of disease) including pathological lymph nodes should be identified as non-target lesions and should also be recorded at baseline. Measurements are not required and these lesions should be followed as 'present', 'absent', or in rare cases 'unequivocal progression' (more details to follow). In addition, it is possible to record multiple non-target lesions involving the same organ as a single item on the case record form (e.g. 'multiple enlarged pelvic lymph nodes' or 'multiple liver metastases').

7.1.3 **Guidelines for Evaluation of Measurable Disease**

All measurements should be recorded in metric notation, using calipers if clinically assessed. All baseline evaluations should be performed as close as possible to the treatment start and never more than 4 weeks before the beginning of the treatment.

The same method of assessment and the same technique should be used to characterize each identified and reported lesion at baseline and during follow-up. Imaging based evaluation should always be done rather than clinical examination unless the lesion(s) being followed cannot be imaged but are assessable by clinical exam.

Clinical lesions: Clinical lesions will only be considered measurable when they are superficial and >10mm diameter as assessed using calipers (e.g. skin nodules). For the case of skin lesions, documentation by color photography including a ruler to estimate the size of the lesion is suggested. As noted above, when lesions can be evaluated by both clinical exam and imaging, imaging evaluation should be undertaken since it is more objective and may also be reviewed at the end of the study.

Chest X-ray: Chest CT is preferred over chest X-ray, particularly when progression is an important endpoint, since CT is more sensitive than X-ray, particularly in identifying new lesions. However, lesions on chest X-ray may be considered measurable if they are clearly defined and surrounded by aerated lung.

CT, MRI: CT is the best currently available and reproducible method to measure lesions selected for response assessment. This guideline has defined measurability of lesions on CT scan based on the assumption that CT slice thickness is 5mm or less. When CT scans have slice thickness greater than 5 mm, the minimum size for a measurable lesion should be twice the slice thickness. MRI is also acceptable in certain situations (e.g. for body scans).

Ultrasound: Ultrasound is not useful in assessment of lesion size and should not be used as a method of measurement. Ultrasound examinations cannot be reproduced in their entirety for independent review at a later date and, because they are operator dependent, it cannot be guaranteed that the same technique and measurements will be taken from one assessment to the next. If new lesions are identified by ultrasound in the course of the study, confirmation by CT or MRI is advised. If there is concern about radiation exposure at CT, MRI may be used instead of CT in selected instances.

Endoscopy, laparoscopy: The utilization of these techniques for objective tumor evaluation is not advised. However, they can be useful to confirm complete pathological response when biopsies are obtained or to determine relapse in trials where recurrence following complete response or surgical resection is an endpoint.

Cytology, Histology: These techniques can be used to differentiate between PR and CR in rare cases if required by protocol (for example, residual lesions in tumor types such as germ cell tumors, where known residual benign tumors can remain). When effusions are known to be a potential adverse effect of treatment (e.g. with certain taxane compounds or angiogenesis inhibitors), the cytological confirmation of the neoplastic origin of any effusion that appears or worsens during treatment can be considered if the measurable tumor has met criteria for response or stable disease in order to differentiate between response (or stable disease) and progressive disease.

